### **Study C (see flow sheet below).**

Following completion of the OGTT (Visit 7), subjects will be started on Bydureon, 2 mg sc per week. Subjects will return of interim follow up visits at weeks 6, 8, 10, 13-14, (visits 8, 9,10, 11. During the weeks 16-18 (visit 12),subjects will have a repeat Double Tracer OGTT (visit 12) will be performed..

**Visits 8, 9, 10, and 11. Brief Follow Up Visits** for interim medical history and compliance with the Bydureon regimen.

**Visit 12: Double Tracer OGTT** will be performed as per **Visit 3**.

The treatment period could be extended based upon the circumstances (based upon the situation of COVID-19 pandemic) until the repeat studies are completed.

**Data Analysis:** In **Study B**, we anticipate that dapagliflozin and Byetta will produce similar reductions in HbA1c and that the combination of dapagliflozin plus Byetta will produce an additive/near-additive reduction in A1c. We anticipate that both dapagliflozin and Byetta monotherapy will produce significant weight loss and that the combination will produce an additive, even synergistic, effect on weight loss.

We anticipate that that the dapagliflozin-induced rise in EGP will persist after 1 month in T2DM patients receiving dapagliflozin monotherapy even though both beta cell function and peripheral insulin sensitivity improve. We expect that Byetta-treated T2DM patients will experience a reduction in both fasting and postprandial plasma glucose levels during the DT-OGTT, markedly enhanced beta cell function, improved peripheral tissue insulin sensitivity, and reduced fasting and postprandial plasma glucagon concentrations during the DT-OGTT. In T2DM patients receiving combined Byetta/dapagliflozin therapy, we hypothesize that exenatide will block the dapagliflozin-induced rise in glucagon secretion and overcome the dapagliflozin-induced decrease insulin secretion, resulting in a greater suppression of EGP. Because we anticipate that Byetta will offset the negative effects of dapagliflozin on EGP and on insulin and glucagon secretion, we expect that the decline in fasting and postprandial glucose concentrations during the DT-OGTT will be enhanced in T2DM subjects receiving combination Byetta/dapagliflozin therapy.

**Sample Size Calculation:** In our published results (10), the difference in the rate of basal EGP during the last hour of EGP measurement in dapagliflozin-treated and placebo-treated individuals was  $0.70 \pm 0.34$  (mean  $\pm$ SD). To detect a 50% decrease in the difference at alpha = 0.167 ( $=0.5/3$ ) (split for 3 comparisons and a Bonferroni correction) in Byetta plus dapagliflozin versus dapagliflozin alone, we computed that 13 subjects in each group will provide 90% power.

**Data Analysis:** In **Study C**, we anticipate that dapagliflozin and Bydureon will produce similar reductions in HbA1c and that the combination of dapagliflozin plus Bydureon will produce an additive/near-additive reduction in A1c. We anticipate that both dapagliflozin and Bydureon monotherapy will produce significant weight loss and that the combination will produce an additive, even synergistic, effect on weight loss.

We anticipate that that the dapagliflozin-induced rise in EGP will persist after 4 months in T2DM patients receiving dapagliflozin monotherapy even though both beta cell function and peripheral insulin sensitivity improve. We expect that Bydureon-treated T2DM patients will experience a reduction in both fasting and postprandial plasma glucose levels during the OGTT, markedly enhanced beta cell function, improved peripheral tissue insulin sensitivity, and reduced fasting and postprandial plasma glucagon concentrations during the DT-OGTT. In T2DM patients receiving combined Bydureon-dapagliflozin therapy, we hypothesize that exenatide will block the dapagliflozin-induced rise in glucagon secretion and overcome the dapagliflozin-induced decrease insulin secretion, resulting in suppression of EGP. Because we anticipate that Bydureon will offset the negative effects of dapagliflozin on EGP and on insulin and glucagon secretion, we expect that the decline in fasting and postprandial glucose concentrations during the DT-OGTT will be enhanced in T2DM subjects receiving combination Bydureon/dapagliflozin therapy.

**Sample Size Calculation:** In our published results (10), the difference in the rate of basal EGP during the last hour of EGP measurement in dapagliflozin-treated and placebo-treated individuals was  $0.70 \pm 0.34$  (mean  $\pm$ SD). To detect a 50% decrease in the difference at alpha = 0.167 ( $=0.5/3$ ) (split for 3 comparisons and a Bonferroni correction) in Bydureon plus dapagliflozin versus dapagliflozin alone, we computed that 13 subjects in each group will provide 90% power.

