**Effect of Chronic Exenatide Therapy on Beta Cell Function and Insulin Sensitivity in T2DM**

## **Study A.**

**Subjects:** 80 T2DM subjects (age = 18-70 years; BMI = 21-45 kg/m^2; male or female) according to the ADA criteria will participate in the study. Subjects must be drug naïve and/or on a stable dose (more than 3 months) of metformin and/or sulfonylurea and have HbA1c >7.0% and <10.5%. Subjects taking drugs known to affect glucose metabolism (other than metformin and sulfonylurea) will be excluded. Other than diabetes, subjects must be in good general health as determined by physical exam, medical history, blood chemistries, CBC, TSH, EKG and urinalysis. Only subjects whose body weight has been stable ( $\pm$  3 lbs) over the preceding three months and who do not participate in an excessively heavy exercise program will be included. Individuals with evidence of proliferative diabetic retinopathy, plasma creatinine >1.4 females or >1.5 males will be excluded. Diabetic subjects will be recruited from the South Texas Veterans Health Care System and Texas Diabetes Institute (TDI) in San Antonio (Deputy Director = [name]). TDI is the largest institute in the United States that provides comprehensive care for ~ 10,000 unduplicated T2DM patients. Therefore, we do not anticipate any problem in recruiting the required number of patients for this study.

**Study design:** After screening, eligible subjects will receive a measurement of endogenous glucose production (EGP) with a prime-continuous infusion of 3-H-glucose. The EGP measurement will be performed in the morning after a 10-12 hour overnight fast and will last 8.5 hours (from 6 AM to 2:30 PM). After a 3.5-hour tracer equilibration period, subjects (20 per group) will receive one of the following medications: (i) placebo; (ii) exenatide 5 ug subcutaneously; (iii) dapagliflozin (10 mg); and (iv) dapagliflozin 10 mg plus exenatide 5 ug (see flow diagram on page 11). Following the test medication at 9:30 AM, blood samples will be drawn every 10-20 minutes for an additional 5 hours and plasma glucose, insulin, C-peptide, glucagon concentrations and glucose specific activity will be measured. One-two weeks after the EGP measurement, participants will come back for the Double Tracer Oral Glucose Tolerance Test (DT-OGTT).

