### **Study B (see flow sheet below)**

Following the measurement of endogenous glucose production [EGP] in Study A, and after the double tracer OGTT visit, subjects who receive Byetta will be started on Byetta, 5 ug sc bid, and they will return for a follow up visit in 7 days (visit 4) at which time the Byetta will be increased to 10 ug sc bid, if tolerated. Subjects will return at days 14, 21, and 28 (visits 5, 6, and 7). If the Byetta dose cannot be increased to 10 ug bid because of side effects on the day 7 visit, the dose will be advanced on the subsequent visit (i.e., day 14 or 21 or 28), side effects permitting. On the day 28 visit the Double Tracer OGTT will be repeated with Byetta dosing at time zero of study (Visit 7).

Subjects who received dapagliflozin will continue on dapagliflozin, 10 mg/day, and will return for follow up visits at days 7, 14, and 21. At the day 28 visit the the DT-OGTT will be repeated. On the day of DT-OGTT, dapagliflozin will be given in the morning prior to the study. Note that this group will not receive Byetta and, thus, will allow us to determine how long the effect of dapagliflozin to increase EGP persists.

Subjects who received dapagliflozin plus Byetta will continue on dapagliflozin and Byetta, and will return for follow up visits at days 7, 14, and 21. At the day 28 visit the DT-OGTT will be repeated. On the day of the DT-OGTT, dapagliflozin will be given in this group will allow us to determine whether the ability of Byetta to inhibit the paradoxical rise in EGP observed with dapagliflozin can be blocked on a chronic basis.

Subjects who received the placebo will not be continued forward. However, these subjects will be allowed to be randomized to the Byetta alone, dapagliflozin alone, or Byetta/dapagliflozin groups.

**Visits 4, 5 and 6: Brief Follow Up Visits** for interim medical history and compliance with the treatment regimen a BMP will be done to check on your kidney function.

**Visit 7: Double Tracer OGTT** will be performed as per **Visit 3**.

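### The 90% power with 13 per group stated for Studies B and C is not shown to apply to them: its inputs come from Study A's basal EGP setting, and no EGP endpoint, effect or SD is given for the DT-OGTT that B and C run

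*Combined protocol and SAP*

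**What the plan says.** The sample-size paragraphs for Studies B and C use the inputs of the Study A paragraph. Each starts from the published result that "the difference in the rate of basal EGP during the last hour of EGP measurement in dapagliflozin-treated and placebo-treated individuals was" 0.70 ± 0.34 (mean ± SD). Each continues "To detect a 50% decrease in the difference at alpha" = 0.167, described as "split for 3 comparisons and a Bonferroni correction", and concludes "we computed that 13 subjects in each group will provide 90% power". Only the name of the exenatide product differs between the two.

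The measurements are set out elsewhere:

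- **Study A.** The primary end point is the change in EGP. The effect is read from minutes 240-300 of the tritiated-glucose turnover study, which is done fasting with one test dose (Study A, Study design; Data Analysis and Statistical Methods).
- **Study B.** "On the day 28 visit the Double Tracer OGTT will be repeated with Byetta dosing at time zero of study" is the only tracer test after treatment starts. The placebo group is not carried forward as placebo, but its members may be randomized to an active group.
- **Study C.** At weeks 16-18 "subjects will have a repeat Double Tracer OGTT (visit 12) will be performed".
- **DT-OGTT.** The sampling table starts the tritiated glucose at -180 min, samples from -60 to 0 min, and gives 75 g glucose with the second tracer at time zero.

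The only declared primary end point is for Study A. The Data Analysis paragraphs for B and C list expected results and name no EGP endpoint, window or test.

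**The concern.** A power statement holds for a particular endpoint, contrast and variance. Here the effect and the SD describe basal EGP in the last hour of measurement, dapagliflozin against placebo. The Anticipated Results text for Study A expects EGP to fall progressively on placebo and, after an initial decline, to rise progressively on dapagliflozin. By the plan's own account, then, the 0.70 depends on the time since dosing and on the placebo decline. Neither condition carries over automatically to a DT-OGTT after 1 or 4 months of daily treatment.

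Studies B and C carry the questions of whether the dapagliflozin effect on EGP persists and whether exenatide blocks it chronically. With no endpoint fixed, basal, post-load or whole-test EGP could be chosen after the data are seen. A null result could also be read as strong evidence against an effect, on the strength of a 90% figure that nothing supports for that measure.

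**Working it through.** **Inputs.** Reference difference 0.70, SD 0.34, halving of the difference, alpha 0.167, 13 per group and 90% power all come from the Study B and Study C sample-size paragraphs. Entry is 20 per group ("subjects (20 per group) will receive one of the following medications"). Study A assumes 15% loss; B and C state none. The tests are taken as two-sided and 0.34 as a between-subject SD; the plan states neither.

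**Step 1: target difference.** 0.50 × 0.70 = 0.35.

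**Step 2: reproduce the plan's figure.** Two-sample normal formula: n = 2 × [(z for alpha/2 + z for power) × SD / difference]².

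- At the literal alpha of 0.167: 2 × [(1.382 + 1.282) × 0.34 / 0.35]² = 13.4, so 14 per group. Power at 13 is 0.893 (0.883 by noncentral t). The stated 13 at 90% is reproduced to within one subject.
- A second route also gives 13. A one-sample formula at 0.05/3 gives [(2.394 + 1.282) × 0.34 / 0.35]² = 12.75. The plan does not say which was used.

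So this point does not turn on the arithmetic.

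**Step 3: compare the powered quantity with what B and C measure.**

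| | Behind the 0.70 and 0.34 | Available in B and C |
|---|---|---|
| Test | EGP measurement as in Study A | DT-OGTT only |
| Basal window | last hour of measurement (240-300 min in Study A) | -60 to 0 min |
| Minutes 240-300 | fasting in Study A | after 75 g glucose |
| Treatment on the test day | one test dose in Study A | about 1 or 4 months of treatment |
| Effect and SD given | yes | none |

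**Step 4: effect of the SD alone.** Two-sample noncentral t, noncentrality = 0.35 / (SD × √(2/13)), 24 degrees of freedom. Every SD other than 0.34 is an assumption.

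| SD | Noncentrality | Power, alpha 0.167 | Power, alpha 0.05/3 |
|---|---|---|---|
| 0.25 | 3.57 | 98% | 83% |
| 0.34 | 2.62 | 88% | 53% |
| 0.45 | 1.98 | 71% | 30% |
| 0.60 | 1.49 | 53% | 16% |

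The alpha 0.167 column isolates the endpoint mismatch. The last column adds the separate correction of alpha from 0.5/3 to 0.05/3.

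**Step 5: effect of the difference alone.** With SD 0.34, alpha 0.167 and 13 per group, by the normal formula, power is 0.893 at a difference of 0.35, 0.721 if the difference is 25% smaller (0.2625), and 0.472 if it is halved (0.175).

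**Step 6: what the arms could detect.** At 90% power and two-sided 0.05/3, by noncentral t, in SD units of whichever endpoint is chosen:

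- 17 per arm (20 × 0.85): 1.32 SD
- 20 per arm: 1.21 SD
- 26 per arm (all 20 placebo subjects re-randomised, 20 + 20/3 = 26.7, rounded down, no loss): 1.05 SD

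If the SD were 0.34, these would be 1.32 × 0.34 = 0.45, 1.21 × 0.34 = 0.41 and 1.05 × 0.34 = 0.36, against the target of 0.35.

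**The case against.** The best defence is that the sample-size text says basal EGP in the last hour of measurement and does not mention minutes 240-300. The DT-OGTT infuses tracer from -180 min and samples from -60 to 0 min, so basal EGP is measured in B and C. If it had the same difference and SD, the stated power would carry over. This stands in part: a reader might infer that B and C cannot produce a basal EGP value, and the documents do not support that. But the plan never says this window is the endpoint, and gives no reason to expect 0.70 and 0.34 there. The window closes as Byetta is injected, and the sampling table places dapagliflozin at -30 min, inside it.

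Three other strong readings should be set aside:

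- **That the missing placebo arm invalidates the comparison.** The powered contrast is the combination against dapagliflozin alone, which needs no placebo arm; 0.70 only sets the target of 0.35.
- **That the mismatch lowers power from 90% to 53%.** At SD 0.34 that fall comes from correcting alpha and from reading 0.34 as a between-subject SD. If 0.34 is the SD of a paired difference, 53% is not the baseline.
- **That B and C are shown to be underpowered.** Nothing in the documents says whether the DT-OGTT SD is above or below 0.34, and a smaller one would raise power.

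The cited publication was not available and the flow sheets for B and C are not shown, so the comparison rests on the text. That the published difference is an acute, single-dose one is inferred from how the Anticipated Results paragraph uses it.

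**Conclusion.** The point holds in this form: the 90% power with 13 per group is not shown to apply to Study B or Study C. Its effect and SD are carried over from a different test setting without justification, and B and C have no defined EGP endpoint to which any power could be attached. The missing endpoint is the deeper gap.

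No single corrected power exists, because the documents give no effect or SD for DT-OGTT EGP. Over assumed SDs of 0.25 to 0.60, power at the literal alpha runs from 98% down to 53%; at 0.05/3 it runs from 83% down to 16%. These ranges assume a difference of 0.35, two-sided tests and between-subject SDs. The point remains after the alpha is corrected. It should be fixed because it is cheap and because the plan relies on the figure, but it does not show that B or C must fail.

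**What to change.** 1. Name one EGP endpoint and window from the DT-OGTT for Studies B and C, for example basal EGP from -60 to 0 min or mean EGP from 0 to 300 min, and state the contrast and test.
2. Reconcile the two statements on test-day dapagliflozin: the Study B text has it given in the morning before the study, while the DT-OGTT sampling table shows it at -30 min. Until they agree, the state of treatment in the basal window is not well defined.
3. Remove the 90% power sentences from the Study B and Study C sample-size paragraphs. Replace them with the detectable difference, at the corrected alpha, for the number per arm actually expected, including re-randomised placebo subjects and expected losses.
4. Convert that difference to EGP units with the SD of the chosen endpoint at Visit 3, which is collected before Study B treatment with the same test. Say that this only approximates the on-treatment SD and is not the SD of a change from baseline.

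The cost is wording and one SD calculation, with no new visits or subjects. The downside is that the stated power becomes less favourable.

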**Data Analysis and Statistical Methods:** The **primary end point** of the study is the change in EGP during **Study A**. The difference in the rate of EGP during the last hour of the study (i.e. from 240-300 minutes) between drug-treatment and placebo-treatment studies represents the effect of drug treatment on EGP. The difference in EGP will be compared among the 3 drug treatments (exenatide, dapagliflozin, and exenatide plus dapagliflozin) with ANOVA. Post hoc testing will be performed with a Bonferroni correction for multiple

comparisons. The following primary comparison will be performed: (i) the change in EGP above baseline following dapagliflozin alone versus dapagliflozin/exenatide. The following secondary comparisons will be made: (i) the change in EGP above baseline following exenatide alone versus dapagliflozin/exenatide and (ii) the change in EGP above baseline following dapagliflozin alone, exenatide alone, and dapagliflozin/exenatide versus the change in EGP following placebo. Between group comparisons will be made with repeated measures ANOVA with time and treatment group as factors.

**Other secondary end points** will be: (i) the decrement in the fasting plasma glucose conc at the end of the study compared to baseline, (ii) change in plasma glucagon conc at the end of the study compared to baseline; and (iii) change in plasma insulin conc at the end of the study compared to baseline. Secondary end points will be compared using the same statistical methods described for the primary end point.

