**Anticipated Results and Data Interpretation.** Consistent with our published data (10), we anticipate that EGP will decrease progressively following placebo administration while, after an initial decline, EGP will increase progressively following dapagliflozin. We anticipate that plasma glucagon conc will increase and plasma insulin concentration will decrease following dapagliflozin administration. We anticipate that a single administration of exenatide will cause an increase in plasma insulin conc and a decrease in plasma glucagon conc compared to placebo. The increase in plasma insulin and decrease in plasma glucagon conc following exenatide administration will result in a greater decline in both EGP and fasting plasma glucose conc compared to placebo. Most importantly, we anticipate that the increase in plasma glucagon conc, the decrease in plasma insulin conc, and rise in EGP following dapagliflozin administration will be prevented, at least in part, if not totally, when exenatide is co-administered with dapagliflozin. Therefore, we anticipate an additive, even synergistic, decrease in plasma glucose conc and EGP following co-administration of dapagliflozin plus exenatide compared to either drug alone.

**Sample Size Calculation:** In our published results (10), the difference in the rate of basal EGP during the last hour of EGP measurement in dapagliflozin-treated and placebo-treated individuals was  $0.70 \pm 0.34$  (mean  $\pm$  SD). To detect a 50% decrease in the difference at alpha = 0.005 ( $=0.5/10$ ) (split alpha for up to 10 multiple comparisons and a Bonferroni correction) in exenatide plus dapagliflozin versus dapagliflozin alone, we computed that 17 subjects in each group provided 90% power. To ensure 17 completers assuming 15% lost to follow-up, we have set the sample size at 20 ( $=17/0.85$ ) in each group.

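### The Bonferroni level for Studies B and C is printed as 0.167 (0.5/3); splitting 0.05 over three comparisons gives 0.0167

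*Combined protocol and SAP*

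**What the plan says.** All three sample-size paragraphs start from the same published result: a dapagliflozin-placebo difference in endogenous glucose production of 0.70 ± 0.34 (mean ± SD). All three aim to detect a halving of that difference with 90% power. They differ in the significance level and the resulting group size.

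- **Study A, Sample Size Calculation:** "To detect a 50% decrease in the difference at alpha = 0.005", with 0.5/10 in brackets, explained as "split alpha for up to 10 multiple comparisons and a Bonferroni correction". The result is "we computed that 17 subjects in each group provided 90% power". Allowing for 15% loss, "we have set the sample size at 20" per group.
- **Studies B and C, Sample Size Calculation** (both paragraphs stand under the Study C heading, the one for Study B first): "To detect a 50% decrease in the difference at alpha = 0.167", with 0.5/3 in brackets, explained as "split for 3 comparisons and a Bonferroni correction". The result is "we computed that 13 subjects in each group will provide 90% power". No dropout allowance is given.

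For analysis, the Study A methods say "Post hoc testing will be performed with a Bonferroni correction for multiple" comparisons, without a number. The Data Analysis paragraphs for Studies B and C describe expected results and name neither a test nor a level. The documents do not say whether tests are one- or two-sided, or whether 0.34 is the SD within one arm or the SD of a difference.

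**The concern.** A Bonferroni split over three comparisons at 0.167 each corresponds to a family level of 0.50, which no part of the plan states. Study A's 0.005 for ten comparisons points to 0.05. Two things are at stake. First, an analyst who looks in the plan for the Study B and C threshold finds only 0.167. Second, if 0.167 had also been used in the calculation, the 13 per group would be too small for a test at 0.0167, so the group sizes have to be checked and not only the printed level.

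**Working it through.** **Inputs.** Difference to detect: 50% of 0.70 = 0.35. Power 90%, so z = 1.282. Equal groups. Stated sizes: 17 (A) and 13 (B and C). Both one- and two-sided tests are tried. The arm SD is taken either as 0.34, or as 0.34/√2 = 0.24 if 0.34 is the SD of a difference.

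**1. The level.** Study A: 10 × 0.005 = 0.05, so the base is 0.05. Its bracket is also wrong, because 0.5/10 = 0.05, not 0.005. Studies B and C: 0.5/3 = 0.167, whereas 0.05/3 = 0.0167.

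**2. Which level produced the 13? A check that does not need the SD.** By normal theory, n per group = 2·SD²·(z_α + z_β)²/difference². With the same SD, difference and power in all three studies, the ratio of sample sizes depends only on alpha and sidedness.

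| | (z_α + z_β)² at 0.005 | at 0.0167 | at 0.167 | ratio 0.005 : 0.0167 | ratio 0.005 : 0.167 |
|---|---|---|---|---|---|
| Two-sided | (2.807 + 1.282)² = 16.72 | (2.394 + 1.282)² = 13.51 | (1.382 + 1.282)² = 7.10 | 1.24 | about 2.4 |
| One-sided | 14.88 | 11.63 | 5.05 | 1.28 | about 2.9 |

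The stated ratio is 17/13 = 1.31. Because both sizes are rounded up, the unrounded ratio may lie anywhere from 16/13 = 1.23 to 17/12 = 1.42. The pair 0.005 and 0.0167 falls in that range; the pair 0.005 and 0.167 is far outside it. With the exact two-sample t-test, one common arm SD returns 17 and 13 together at 0.005 and 0.0167 (0.226–0.227 two-sided, 0.243–0.249 one-sided). No common SD does so at 0.005 and 0.167.

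**3. Reproducing the plan's group sizes (two-sided, normal formula / t-test).**

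| Arm SD | A at 0.005 (stated 17) | B, C at 0.0167 (stated 13) | B, C at 0.167 (stated 13) |
|---|---|---|---|
| 0.24 | 16 / 18 | 13 / 15 | 7 / 8 |
| 0.34 | 32 / 34 | 26 / 27 | 14 / 14 |

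For example, with arm SD 0.24 at 0.0167: 2 × (0.34²/2) × 13.51/0.35² = 12.75, rounded up to 13. Only arm SD 0.24 with 0.005 and 0.0167 comes close to both stated sizes.

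**4. Power at 0.0167, difference 0.35.**

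| Arm SD and test | 13 per arm | 17 | 20 |
|---|---|---|---|
| 0.24, two-sided t | 86% | 95% | 98% |
| 0.24, one-sided t | 92% | 97.5% | 99% |
| 0.24, two-sided normal | 90.6% | 96.8% | 98.6% |
| 0.34, two-sided t | 53% | 68% | 77% |

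With arm SD 0.24 and the error pooled over three arms, as in an ANOVA, power at 13 per arm is 87.9%.

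**5. If 0.167 were the test level.** In a simulation of three pairwise t-tests among three arms (200,000 runs; these are assumed to be the three comparisons), the chance of at least one false positive is about 35%. The Bonferroni bound is 3 × 0.167 = 0.50. At 0.0167 the simulated figure is about 4.4%.

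**The case against.** The strongest reply is that this is a misplaced decimal with almost no consequence. With arm SD 0.24, the stated 13 is exactly what the two-sided normal formula gives at 0.0167 (90.6% power), and a one-sided t-test also gives 13. The 86% is the lowest of the four figures on that reading. Study A enrols 20 per arm for 17 completers, and placebo subjects may be randomized into the active groups for Study B, so 13 is a requirement with room above it. No text calls 0.167 the test level, so the 35% is hypothetical.

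Most of this stands: on the better-supported reading the loss of power is at most a few points. It does not remove the error, because 0.167 is the only level the plan offers for Studies B and C.

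A second reply is that the printing slip is inferred, not proven. Taken alone, 13 nearly fits the printed 0.167 if 0.34 is a per-arm SD (n = 14 two-sided; 88% power at 13). The slip would then have entered the calculation, and 26–27 per group would be needed at 0.0167. Study A's bracket read literally, as one-sided 0.05 with arm SD 0.34, also gives exactly 17. These points are fair, but neither explains both sizes consistently. Arm SD 0.34 gives Study A only 50–58% two-sided power at 17 per group and 0.005 (61% with a one-sided t-test). Pairing one-sided 0.05 for A with 0.167 for B and C needs a two-sided test in B and C, and then gives 14.

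A third reply is that the meaning of the SD and the sidedness are separate omissions that affect Study A equally. That is true, but the 90% cannot be confirmed at the corrected level without them.

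**Conclusion.** The concern holds. The printed level of 0.167 is ten times too large; given the base of 0.05 implied by Study A, it should be 0.0167. That part is certain as a matter of arithmetic. That the error is in the printing and not in the calculation is a well-supported inference, resting on the 17 and 13 taken together and on all three studies sharing one SD, difference and power.

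On that reading the effect on power is small: 86–92% at 13 per arm, depending on the test, against the stated 90%, and 95% or more at 17. If 0.34 is instead a per-arm SD, two-sided power at 13 falls to 53%, but Study A's own figure then fails as well. The inflated family error arises only if someone tests at 0.167. This should be fixed because it is the only threshold given for two of the three studies.

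**What to change.** 1. In the sample-size paragraphs for Studies B and C, print alpha = 0.0167 (=0.05/3), and state that 0.0167 is the test level for the three comparisons in each study. In Study A, change the bracket to 0.05/10; the 0.005 stays.
2. State whether 0.34 is a per-arm SD or the SD of a difference, and whether the tests are one- or two-sided.
3. Restate power at 0.0167 on that basis, naming the test used. The power table above gives the figures for either SD.

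The cost is wording in three paragraphs and two definitions. The stated power may come out lower, for example 86% instead of 90% at 13 per arm with a two-sided t-test and arm SD 0.24. No extra patients are needed for the correction itself.

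### Once the family alpha is set at 0.05, Holm or a three-arm closed test would be a cheap, mostly modest improvement on the Bonferroni correction

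*Combined protocol and SAP*

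**What the plan says.** Under Study A, Data Analysis and Statistical Methods, the three drug treatments are compared by ANOVA, and then "Post hoc testing will be performed with a Bonferroni correction". The Study A sample-size paragraph describes its level as "split alpha for up to 10 multiple comparisons and a Bonferroni correction".

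For Studies B and C, Bonferroni appears only in the Sample Size Calculation paragraphs (the Byetta paragraph for B and the Bydureon paragraph for C, both printed under the Study C heading). Each sets a level of 0.167, written as 0.5/3, and explains it as "split for 3 comparisons and a Bonferroni correction". The target is "To detect a 50% decrease in the difference", which for Study B is "in Byetta plus dapagliflozin versus dapagliflozin alone". The conclusion is "we computed that 13 subjects in each group will provide 90% power".

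The Data Analysis paragraphs for B and C describe expected results. They name no test, do not list the three comparisons and state no multiplicity procedure. Enrolment is 20 per group, to give 17 completers.

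**The concern.** Single-step Bonferroni tests every comparison at alpha/3, whatever the other comparisons show. Two standard alternatives control the same family error and are never less powerful here: Holm's step-down test and, for exactly three arms, a closed test that starts with an overall F test.

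The protocol already places an ANOVA of three drug treatments ahead of the Bonferroni step in Study A. If that sequence is carried into B and C, the Bonferroni step after a three-arm F test is not needed for error control. At stake is some power for combination versus dapagliflozin alone, which could be had without more patients.

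**Working it through.** **Inputs from the documents.** Reference difference 0.70 with SD 0.34; effect to detect 50% of 0.70 = 0.35; 13 per group for 90% power; 20 enrolled and 17 completers per group. The text does not say whether 0.34 is the SD within an arm or the SD of a difference. In the second case the arm SD is 0.34/√2 = 0.24.

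**The plan's own 13.** For a two-sided, two-sample comparison, n = 2(SD/Δ)²(z₁₋α/₂ + z₀.₉)², with (0.34/0.35)² = 0.944.
- Printed level 0.167: 2 × 0.944 × (1.382 + 1.282)² = 13.4. At n = 13 the power is 89%, so the printed level reproduces the stated figure closely.
- Level 0.05/3 = 0.0167, arm SD 0.34: 2 × 0.944 × (2.393 + 1.282)² = 25.5, so 26 per group.
- Level 0.0167, with 0.34 as the SD of a difference: half of that, 12.7, so 13.

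The figure 13 therefore has two readings, and they imply different arm SDs.

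**Why the closed test is valid.** With three arms, if any two pairwise nulls are true, all three means are equal. Call a pair different only if the F test and that pair's test both reject at 0.05.
- All means equal: an error requires the F test to reject, probability 0.05.
- Exactly one pair equal: an error requires that pair's test to reject, probability at most 0.05.
- No pair equal: no error is possible.

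Holm tests the ordered p-values at alpha/3, alpha/2 and alpha, so it rejects everything Bonferroni rejects.

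**Simulation.** Normal data, equal arms, common SD, pooled three-arm variance, family alpha 0.05, with 60,000 to 200,000 trials per scenario agreeing within about one point.

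Under the global null, family error is 4.3% for Bonferroni and Holm and 4.9% for the closed test. With one pair truly equal, it is 1.6-1.8% for Bonferroni and 4.8-5.1% for the closed test.

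For power, the means relative to placebo are dapagliflozin 0.70 and combination 0.35. The exenatide-alone mean is not in the documents; it is assumed between -0.2 and 0.525, where 0.525 = (0.70 + 0.35)/2 is the least favourable value tried.

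| Arm SD | n per arm | Bonferroni | Holm | Closed |
|---|---|---|---|---|
| 0.34 | 17 | 70% | 71-84% | 73-84% |
| 0.34 | 20 | 78% | 79-89% | 81-89% |
| 0.24 | 17 | 96% | 96-99% | 97-99% |

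The low end of each range is the midway case, where Holm gains about one point or less. The high end applies when exenatide alone is at or below placebo. With arm SD 0.24 and n = 20, Bonferroni already gives 98%, so no procedure can add more than 2 points.

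**Against the printed level.** A family-0.05 Holm or closed test never tests a pair above 0.05. At n = 13 and arm SD 0.34, the power at 0.05 is 75%, against 89% at 0.167. The printed levels sum to 3 × 0.167 = 0.50, with a simulated family error of about 34%.

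**The case against.** The strongest reply is that Bonferroni is a valid, conservative choice, so this is a preference and not an error. That stands: Bonferroni gives simple simultaneous intervals that match the test decisions, and it does not need the common-variance assumption of the pooled F-gated test.

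Four further points also stand.
- A reader might infer that Studies B and C will be analysed by single-step Bonferroni. The documents do not say so. The split appears there only to set the sample size, and alpha/3 is also a safe planning level for Holm, whose first step is alpha/3. For the same reason Holm guarantees no smaller sample size.
- All pairs of three active arms is an inference. The listed pairs under Study Design are for the initial turnover study only. For Study C, the text starts subjects on Bydureon without separating arms, while its Data Analysis paragraph expects dapagliflozin monotherapy. Those passages must be reconciled before a three-arm argument can be relied on.
- Thirteen per arm is the stated requirement, not the planned number. The relevant sizes are 17 to 20, and former placebo subjects may be randomized into the active groups as well.
- The size of the gain depends on an exenatide-alone mean that the documents do not give.

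In reply, the protocol's Anticipated Results for Study A expect exenatide to lower EGP more than placebo does. If that carries over to B and C, the larger gains apply. The sponsor also has to write the missing analysis section for B and C in any case.

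**Conclusion.** The point holds as an inexpensive improvement, secondary to correcting alpha. At family alpha 0.05 and 17 to 20 per arm, the closed test gains about 3 to 14 points for combination versus dapagliflozin if 0.34 is the arm SD (73 - 70 = 3 to 84 - 70 = 14 at n = 17; 81 - 78 = 3 to 89 - 78 = 11 at n = 20). It gains at most about 3 points if 0.34 is the SD of a difference. Holm gains between about 1 point or less and the same upper figures.

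These results assume exactly three arms, all three pairs as the family, normal data with a common variance, and an exenatide-alone mean between -0.2 and 0.525. No gain was computed for Study A; there the claim is only that Holm cannot do worse than Bonferroni.

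A reader might conclude that Bonferroni is a major source of lost power, or that power is given up for nothing. Neither is supported. Under the SD reading that yields 13 at 0.0167, Bonferroni power is already 96-98% at 17 to 20 per arm, and Bonferroni buys simpler intervals. On the level as printed, moving to a family-0.05 procedure would lower power.

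**What to change.** First correct the level for Studies B and C to a split of 0.05, state what the SD of 0.34 describes, and recompute the sample size. The change proposed here does not do that work.

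Then:
- In Study A, use Holm instead of Bonferroni for the secondary comparisons.
- In Studies B and C, name the three pairwise comparisons and test them at family alpha 0.05 by the closed procedure: an overall three-arm F test at 0.05 on the same EGP measure, then each pair at 0.05 with the pooled variance. If the three-arm structure or a common variance is in doubt, use Holm, which needs neither.
- Report unadjusted 95% confidence intervals alongside, and say that they are unadjusted.

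The cost is SAP wording only, with no extra patients or measurements. The downsides are that confidence intervals will not match the adjusted decisions one to one, and that the F-gated version assumes a common variance.
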